### 6.5.5 Tuberculosis

Tuberculosis is a mycobacterial infectious disease generally presenting as cough with systemic symptoms of infection diagnosed by skin test (purified protein derivative), blood test (IGRA), radiographic imaging, body fluid and tissue sampling; presentation may include disseminated or latent disease. An infection may be new (at least conversion of a TB test to positive) or reactivation of dormant disease (new active disease in a previously TB test positive subject without prior evidence of active disease).

- **A bacteriologically confirmed TB** case is a case where a biological specimen is positive by smear microscopy, culture or rapid diagnostic, such as polymerase chain reaction or nucleic acid amplification test (Xpert MTB/RIF).
- **A clinically diagnosed TB** case is a case where the subject does not fulfil the criteria for bacteriological confirmation, but has been diagnosed with active TB by a clinician or other medical practitioner who has decided to give the subject a full course of TB treatment. This definition includes cases diagnosed on the basis of x-ray abnormalities or suggestive histology and extra-pulmonary cases without laboratory confirmation. Clinically diagnosed cases subsequently found to be bacteriologically positive (before or after starting treatment) should be reclassified as bacteriologically confirmed.

Bacteriologically confirmed or clinically diagnosed cases of TB are also classified according to: anatomical site of disease; history of previous treatment; drug resistance; HIV status ([World Health Organization, 2014](#)).

**Latent TB** is a mycobacterial infection without clinical, bacteriological findings, or radiologic findings consistent with active TB and a TB blood test such as an IGRA (QFT-G) or purified protein derivative skin test that is positive both at the time of provisional diagnosis and on repeat assessment.

Subjects identified with latent TB will be assessed by a local TB specialist to confirm the diagnosis and local SOC that will be used in treatment. Once latent TB is confirmed, treatment must be instituted immediately and no investigational product may be administered until treatment of latent TB has begun. Additionally, subjects with newly diagnosed latent TB must agree to complete a locally recommended course of treatment for latent TB to continue to receive investigational product.

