5. All males (sterilised or non-sterilised) who are sexually active must use a condom (with spermicide where commercially available) for contraception with a woman of child bearing potential from Day 1 until at least 12 weeks after receipt of the final dose of investigational product. It is strongly recommended that female partners of child bearing potential of male subjects use a highly effective method of birth control from [Table 1](#) (other than a barrier method) throughout this period.
6. Females with an intact cervix must have a Pap smear completed and without documented malignancy (eg. no signs of CIN grade III, CIS, or AIS) within 90 days prior to randomization or up until 30 days post-randomization, ie, before IP dosing at V2.  
Subjects with abnormal Pap smear results of atypical squamous cells of undetermined significance (ASC-US), atypical squamous cells where high-grade squamous intraepithelial lesion (HSIL) cannot be ruled out (ASC-H), atypical glandular cells (AGC), or CIN grades I and II (CIN I and II) will be allowed to enter the study [REDACTED].
7. Willing to forego other forms of experimental treatment during the study
8. Meets the following TB criteria:

- (a) **Negative** QuantiFERON®-TB Gold [QFT-G] test result for TB obtained from the study central laboratory at Week 52 of Studies D3461C00004 or D3461C00005

OR

- (b) **Newly positive** QFT-G test result for TB obtained at Week 52 of Studies D3461C00004 or D3461C00005 from the study central laboratory. A chest x-ray must be performed. If the chest x-ray shows no evidence of active TB, and the subject has no symptoms or medical history consistent with active TB, the subject must have a retest. If the retest is positive, the subject must initiate treatment for latent TB within 30 days of randomisation, but prior to the second dose of investigational product administration (Visit 2/Week 4). This should be reported as an AESI.

OR

- (c) **Positive but not newly positive** QFT-G test at Week 52 of Studies D3461C00004 or D3461C00005 from the study central laboratory. The subject must have been diagnosed with latent TB and must have documentation confirming completion of appropriate treatment OR initiate treatment for latent TB within 30 days of randomisation, but prior to the second dose of investigational product administration (Visit 2/Week 4)

OR

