#### 5.2.7.1 Tuberculosis results at time of randomisation/Week 52 of the Phase 3 Study D3461C00004 or D3461C00005

- If the QFT-G test result was **negative** and there is no known history of recent exposure to individuals with active TB, the subject may be randomised.
- If the QFT-G test result was **newly positive**, a chest x-ray must be performed. If the chest x-ray shows no evidence of active TB, and the subject has no symptoms or medical history consistent with active TB, the subject must have a retest. If the retest is positive, the subject must start on prophylaxis within 30 days of randomisation, but prior to the second dose (Visit 2/Week 4) in the LTE study. The subject should be referred to a TB specialist. If a TB specialist is not available, the local country guidelines should be followed for further diagnostic work up and anti-TB treatment regimens. If no local guidelines exist for immunocompromised

individuals, then USA guidelines may be followed. This should be reported as an AESI. The QFT-G test must be repeated annually.

- If the QFT-G test was **positive but not newly positive**, the subject must have been diagnosed with latent TB and must have documentation confirming completion of appropriate OR initiate treatment for latent TB within 30 days of randomisation, but prior to the second dose (Visit 2/Week 4).
- If the QFT-G test result was newly indeterminate (as confirmed on retest unless prior positive QFT-G was documented, along with completed treatment for latent TB) or indeterminate but not newly indeterminate, further QFT-G testing will be done according to the Study Plan ([Table 2](#) and [Table 3](#)).

QFT-G testing is performed at least annually and in some cases more often, depending on the result. Refer to the Study Plan ([Table 2](#) and [Table 3](#)).

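### Inclusion criterion 8(c), and 8(b) when latent TB is confirmed before Day 1, permit a first LTE dose before latent TB treatment starts; Section 6.5.5 prohibits that dose

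*Protocol*

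**What the plan says.** The relevant instructions sit in four sections of the protocol.

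- **Section 6.5.5 (Tuberculosis).** After confirmation of latent TB, treatment has to start at once, and "no investigational product may be administered until treatment of latent TB has begun". Latent TB is defined there by a test that is "positive both at the time of provisional diagnosis and on repeat assessment", and a local TB specialist is to confirm the diagnosis.
- **Section 3.1, criterion 8(b)** (newly positive QFT-G at Week 52 of the feeder study). A chest x-ray and a retest are required. "If the retest is positive, the subject must initiate treatment for latent TB within 30 days of randomisation, but prior to the second dose".
- **Section 3.1, criterion 8(c)** (positive, but not for the first time). "The subject must have been diagnosed with latent TB and must have documentation confirming completion of appropriate treatment"; the alternative is to "initiate treatment for latent TB within 30 days of randomisation, but prior to the second dose of investigational product administration".
- **Section 5.2.7.1.** The newly positive bullet says "the subject must start on prophylaxis within 30 days of randomisation, but prior to the second dose". The next bullet repeats the alternative in 8(c).
- **Section 5.2.7.2.** At each visit the site checks that there is no history of latent TB, except where it was diagnosed and the start of suitable treatment is documented.

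Two timing statements matter as well. Sections 1.4 and 3.6 place the first LTE dose, as a rule, on the day of the Week 52 visit. Section 3.1 needs the Week 52 QFT-G result only before dose 2, so it can still be outstanding when dose 1 is given.

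**The concern.** The entry criteria and 5.2.7.1 attach the start of latent TB treatment to dose 2. Section 6.5.5 attaches it to the next dose after confirmation, whichever dose that is. For a subject whose latent TB is already confirmed on Day 1, these differ by one infusion: the entry text lets dose 1 go ahead, and 6.5.5 does not. They also differ on urgency, since 6.5.5 wants treatment without delay and the entry text gives a 30-day limit.

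This is an instruction written for participant safety. A site working from the eligibility criteria could give dose 1 in good faith and breach a dosing prohibition elsewhere in the same protocol. Another site, working from 6.5.5, would withhold the dose from an identical subject.

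**Working it through.** No sample size, error rate or event count is involved and the plan gives no figure to reproduce. The check sets the rules side by side for each kind of subject.

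**Trigger in 6.5.5.** The bar takes effect on confirmation, which needs a positive repeat test and specialist assessment. It is not confined to cases first found during the LTE. It covers subjects identified with latent TB; only the following sentence, on agreeing to complete a course of treatment, is limited to new diagnoses.

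**Deadline in 3.1 and 5.2.7.1.** Treatment must start within 30 days of randomisation and before Visit 2/Week 4. This is a latest date. Nothing requires dose 1 to come first, and nothing forbids it.

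| Subject at Day 1 | Entry text on dose 1 | Section 6.5.5 on dose 1 | Result |
|---|---|---|---|
| 8(c), latent TB diagnosed, treatment completed | permitted | permitted | agree |
| 8(c), latent TB diagnosed, treatment not started | permitted | barred | conflict |
| 8(b), retest positive and latent TB confirmed before Day 1, treatment not started | permitted | barred | conflict |
| 8(b), latent TB confirmed after Day 1 | permitted | permitted, as not yet confirmed | agree; both require treatment before dose 2 |
| 8(b) or 8(c), treatment started before dose 1 | permitted | permitted | agree |

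**Doses at issue.** The latest start under the entry text falls before dose 2, so the doses that may precede treatment number 2 − 1 = 1. On the scheduled visits that is up to about 4 weeks between the first infusion (Week 0) and the latest start of treatment (before Week 4).

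**Other checks.** The every-visit check in 5.2.7.2 expects documented initiation of treatment. On Day 1 that agrees with 6.5.5 and not with the later deadline in 8(c). The pre-administration list in 7.2.2 asks that the subject was evaluated for signs and symptoms of TB; it does not ask whether latent TB treatment has begun, so it does not settle the matter.

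**The case against.** The strongest reply is that the texts are compatible. The entry criteria give a latest date, 6.5.5 gives a stricter one, and a site that starts treatment before dose 1 complies with both. This is correct. A reader might infer that sites cannot follow both rules, or that whatever a site does breaches one section; the documents do not support that. What remains is that one section permits a dose that another prohibits, and no text says which governs.

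Second, the bar in 6.5.5 depends on confirmation. A reader might take it as forbidding any product before latent TB treatment in all cases, which would put all of 8(b) in conflict. It does not. With dose 1 usually on the Week 52 visit day, the QFT-G result allowed to arrive later, and an x-ray and retest to follow, confirmation under 8(b) may well come after dose 1, and then the sections agree. This stands, and limits 8(b) to confirmation before Day 1.

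Third, 8(c) can be parsed in two ways: the diagnosis may govern both alternatives, or only the one about completed treatment. On the second parsing, a subject who has yet to start treatment need not have been diagnosed before entry. That narrows the conflict under 8(c) to those whose latent TB is in fact confirmed by Day 1, but it does not remove it, and the ambiguity is itself a reason to reword.

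Fourth, the every-visit check in 5.2.7.2 might stop the dose. It might, but it does so by contradicting the 8(c) deadline, which adds a further place to reconcile.

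Last, a reader might link this to the primary outcome, because TB including latent TB is an AESI. The link is weak. The instruction to report as an AESI is attached to the newly positive case and not to 8(c), and events before LTE randomisation belong to the feeder studies. The order of dose 1 and treatment changes no analysis set, estimate or interval method.

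**Conclusion.** The inconsistency is real and confined to two groups: subjects under 8(c) with diagnosed latent TB whose treatment has not started by Day 1, and subjects under 8(b) whose latent TB is confirmed before Day 1 and not yet treated. For them the entry criteria and 5.2.7.1 permit a first LTE dose that 6.5.5 prohibits.

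The size is at most one dose per affected subject. The documents do not give the number of such subjects. Nor should one infer that every untreated 8(c) subject will be dosed before treatment: the text allows that order but does not bring it about. Whether any subject reaches Week 52 with diagnosed, untreated latent TB depends partly on feeder-study rules that these documents do not contain.

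The conclusion rests on reading the bar in 6.5.5 as applying to all confirmed latent TB, which is how it is worded, and on dose 1 being given on or soon after the Week 52 visit. The point matters because it concerns a dosing instruction meant to protect participants. It has no bearing on sample size, error rates or the planned analyses.

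**What to change.** The sponsor should reconcile criteria 8(b) and 8(c) in Section 3.1, the two matching bullets in 5.2.7.1, the every-visit check in 5.2.7.2 and the dosing bar in 6.5.5, so that a single rule governs dosing in relation to the start of latent TB treatment and reads the same in each place. The reconciled text should make three things plain: what event triggers the rule, whether it applies to dose 1, and how soon treatment must start. Criterion 8(c) should also be punctuated so that it is clear whether the prior diagnosis applies to both of its alternatives. The choice of rule is a clinical decision for the sponsor, and this review does not propose one.

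The cost is protocol wording and the amendment process that goes with it. No change to the SAP is needed.

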### 6.5.6 Vasculitis (non-systemic lupus erythematosus)

Vasculitis (non SLE) is defined as an inflammatory disorder of blood vessels involving arteries and/or veins and characterised by characteristic clinical signs/symptoms and diagnosed by biopsy, imaging such as angiography, or blood tests such as findings of antineutrophil cytoplasmic antibodies consistent with the diagnosis. Underlying causes should

be identified, such as medications including study drug, infections, or systemic inflammatory syndromes, wherever possible.

### **6.5.7 Major adverse cardiovascular events**

As a measure of enhanced pharmacovigilance, an independent Cardiovascular Event Adjudication Committee (CV-EAC) will review deaths (due to any cause) and all SAEs in the cardiovascular System Organ Classes for evaluation as to whether to classify as MACE events (stroke, myocardial infarction, or cardiovascular death).

The CV-EAC will review cases of interest to determine if they meet accepted diagnostic criteria. Causality assessments will not be made by the CV-EAC, nor will the committee possess governance authority. The CV-EAC will be blinded regarding any information relating to the randomisation group.

## **6.6 Recording of adverse events**

### **6.6.1 Time period for collection of adverse events**

Adverse events and SAEs will be collected from the time of randomisation, throughout the treatment period, and including the follow-up period until Follow-up Visit 2 (12 weeks post-final dose). Events that occur prior to randomisation in the LTE study should be reported in Studies D3461C0004 or D3461C00005.

### **6.6.2 Follow-up of unresolved adverse events**

Any AEs that are unresolved at the subject's last visit in the study are followed up by the study staff for as long as medically indicated. The Sponsor retains the right to request additional information for any subject with ongoing AE(s)/SAE(s) at the end of the study, if judged necessary.

### **6.6.3 Variables**

The following variables will be collected for each AE;

- AE (verbatim)
- The date and time when the AE started and stopped
- Maximum intensity
- Whether the AE is serious or not
- Investigator causality rating against the investigational product (yes or no)
- Action taken with regard to investigational product
- Outcome of AE

In addition, the following variables will be collected for SAEs:

- Onset Date (Date AE met criteria for serious AE)
- Detection Date (Date Investigator became aware of serious AE)
- AE is serious due to:
  - (a) Death
    - Date of death
    - Autopsy performed
    - Primary/secondary cause of death
  - (b) Life-threatening
  - (c) In-patient hospitalisation or prolongation of existing hospitalisation
    - Date of hospitalisation
    - Date of discharge
  - (d) Congenital abnormality or birth defect
  - (e) Important medical event
  - (f) Suspected transmission via a medicinal product of an infectious agent
- Description of AE
- Investigator causality assessment to concomitant medications
- Investigator causality assessment to study procedures (yes or no)

It is important to distinguish between serious and severe AEs. Severity is a measure of intensity, whereas seriousness is defined by the criteria defined above. An AE of severe intensity need not necessarily be considered serious. For example, nausea that persists for several hours may be considered severe nausea, but not an SAE. On the other hand, a stroke that results in only a limited degree of disability may be considered a mild stroke but would be an SAE. The Investigator should provide an assessment of the severity of each AE/SAE.

#### **6.6.4 Causality collection**

The Investigator will assess causal relationship between investigational product and each AE, and answer 'yes' or 'no' to the question 'Do you consider that there is a reasonable possibility that the event may have been caused by the investigational product?'

For SAEs causal relationship will also be assessed for other medication and study procedures and additional study drug (such as OCS, azathioprine, antimalarials, mycophenolate mofetil/mycophenolic acid, methotrexate, and mizoribine). Note that for SAEs that could be associated with any study procedure the causal relationship is implied as 'yes'.

#### **6.6.5 Adverse events based on signs and symptoms**

All AEs spontaneously reported by the subject or care provider or reported in response to the open question from the study personnel: *'Have you had any health problems since the previous visit/you were last asked?'*, or revealed by observation will be collected and recorded on the CRF. When collecting AEs, the recording of diagnoses is preferred (when possible) to the recording of a list of signs and symptoms. However, if a diagnosis is known and there are other signs or symptoms that are not generally part of the diagnosis, the diagnosis and each sign or symptom will be recorded separately.

#### **6.6.6 Adverse events based on examinations and tests**

The results from protocol-mandated laboratory tests and vital signs will be summarised in the Clinical Study Report. Deterioration as compared to baseline in protocol-mandated laboratory values, vital signs, ECGs, and other safety assessments should therefore only be reported as AEs if they fulfil any of the SAE criteria or are the reason for discontinuation of treatment with the investigational product.

If deterioration in a laboratory value/vital sign is associated with clinical signs and symptoms, the sign or symptom will be reported as an AE and the associated laboratory result/vital sign will be considered as additional information. Wherever possible, the reporting Investigator will use the clinical rather than the laboratory term (eg, anaemia versus low haemoglobin value). In the absence of clinical signs or symptoms, clinically relevant deteriorations in non-mandated parameters should be reported as AE(s).

Deterioration of a laboratory value, which is unequivocally due to disease progression, should not be reported as an AE.

Any new or aggravated clinically relevant abnormal medical finding at a physical examination as compared with the baseline assessment will be reported as an AE (or SAE, as appropriate).

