### **6.1 Definition of adverse events**

An AE is the development of an undesirable medical condition or the deterioration of a pre-existing medical condition following or during exposure to a pharmaceutical product, whether or not considered causally related to the product. An undesirable medical condition can be symptoms (eg, nausea, chest pain), signs (eg, tachycardia, enlarged liver) or the abnormal results of an investigation (eg, laboratory findings, ECG). In clinical studies, an AE can include an undesirable medical condition occurring at any time, including run-in or washout periods, even if no study treatment has been administered.

The term AE is used to include both serious and nonserious AEs.

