### **6.2 Definitions of serious adverse event**

An SAE is an AE occurring during any study phase (ie, run-in, treatment, washout, follow-up), that fulfils 1 or more of the following criteria:

- Results in death
- Is immediately life-threatening
- Requires in-patient hospitalisation or prolongation of existing hospitalisation
- Results in persistent or significant disability/incapacity or substantial disruption of the ability to conduct normal life functions

- Is a congenital abnormality or birth defect
- Is an important medical event that may jeopardise the subject or may require medical intervention to prevent one of the outcomes listed above.

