#### **6.6.7 Disease progression/worsening of systemic lupus erythematosus**

Disease progression can be considered as a worsening of a subject's condition attributable to SLE. It may be an increase in the activity or severity of the existing manifestations of SLE or the appearance of new manifestations. Worsening of SLE should not be reported as an AE, unless the signs and symptoms meet criteria for an SAE.

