## 6.7 Reporting of serious adverse events

All SAEs have to be reported, whether or not considered causally related to the investigational product, or to the study procedure(s). All SAEs will be recorded on the CRF. PRA Safety Management is to be sent all safety forms and supporting documentation including laboratory tests, imaging reports, diagnostic test results, biopsy reports, and discharge summaries.

If any SAE occurs in the course of the study, then Investigators or other site personnel are to inform PRA Safety Management within 1 day, ie, immediately but **no later than 24 hours** after he or she becomes aware of it.

PRA Safety Management works with the Investigator to ensure that all the necessary information is provided to the PRA safety data entry site **within 1 calendar day** of initial receipt for fatal and life-threatening events (if received for instance during a weekend or a public holiday, the information is forwarded as early as possible on the first business day following the weekend or holiday) and **within 3 calendar days** after initial receipt for all other SAEs.

For fatal or life-threatening AEs where important or relevant information is missing, active follow-up is undertaken immediately. Investigators or other site personnel inform PRA Safety Management of any follow-up information on a previously reported SAE within 1 calendar day, ie, immediately but **no later than 24 hours** after he or she becomes aware of it.

Once the Investigators or other site personnel indicate an AE is serious or is an AESI in the Datalabs system, an automated email alert is sent to the designated PRA and AstraZeneca representative(s).

If the Datalabs system is not available, then the Investigator or other study site personnel reports a SAE to PRA Safety Management on the study-specific paper SAE form by telephone, fax, or email. The SAE report form must be completed in the electronic system as soon as the system is available again.

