The event rate per 100 subject years including 95% CIs will be summarised for the following categories. Summaries of AESIs will be presented by AESI category (non-opportunistic serious infections, opportunistic infections, anaphylaxis, malignancy, herpes zoster, tuberculosis, influenza, vasculitis [non SLE], and major acute cardiovascular events) and preferred term. Summaries for SAEs will be presented by MedDRA system organ class and preferred term.

- Any AESI
- Any AESI by time interval for the first onset of event – alternative event rates
- Any AE leading to discontinuation of IP by time interval for the first onset of event – alternative event rates (combined feeder & LTE study, by preferred term)
- Any AESI – alternative event rates
- Any SAE (including events with outcome = death) (during treatment and during follow-up separately. No event rate for during follow-up will be presented)
- Any SAE (including events with outcome = death) by time interval for the first onset of event – alternative event rates

The event rate per 100 subject years will be summarised by MedDRA system organ class and preferred term for the following AE categories.

- Any AE (during treatment and during follow-up separately. No event rate for during follow-up will be presented)
- Any AE by descending preferred term (during treatment, and during the LTE treatment)
- Any AE with outcome = death
- Any SAE by descending preferred term (including events with outcome = death) (during treatment, and during the LTE treatment)
- Any AE leading to discontinuation of investigational product
- Any AE by relationship to investigational product (yes, no) (multiple occurrences of an AE in 1 subjects will only be counted once as related if at least one AE is related and as not related if all occurrences are not related)
- Any AE by maximum intensity (mild, moderate, severe) (i.e., multiple occurrences of an AE in 1 subjects will only be counted once with the maximum intensity in this AE)
- Any other significant AE

The alternative event rate per 100 subject years will be summarised by MedDRA preferred term for the following AE categories.

- Any COVID-19 related AE (for the LTE Study only, only subjects remaining in the study on 11-Mar-2020 will be included)
- Any SAE prior to the COVID-19 pandemic (for the LTE Study only)
- Any SAE during the COVID-19 pandemic (for the LTE Study only, only subjects remaining in the study on 11-Mar-2020 will be included)

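### Protocol 6.6.6 excludes unequivocally lupus-driven laboratory deterioration from AE reporting with no exception for serious events, which conflicts with its own opening rule, with 6.6.7 and with 6.7

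*Protocol*

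**What the plan says.** Four rules in the protocol bear on the same event.

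- **6.6.6, first paragraph.** For worsening laboratory values and other measurements that the protocol mandates, the rule is that they "should therefore only be reported as AEs if they fulfil any of the SAE criteria or are the reason for discontinuation of treatment". Lupus is not carved out.
- **6.6.6, third paragraph.** "Deterioration of a laboratory value, which is unequivocally due to disease progression, should not be reported as an AE". There is no exception for a serious event, nor for one that leads to stopping investigational product.
- **6.6.7.** "Worsening of SLE should not be reported as an AE, unless the signs and symptoms meet criteria for an SAE". The exception is worded for signs and symptoms and does not name laboratory values. It has no counterpart for stopping product.
- **6.7.** "All SAEs have to be reported, whether or not considered causally related to the investigational product".

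Two definitions fix the scope of the word AE. In 6.1, "The term AE is used to include both serious and nonserious AEs". In 6.2, "An SAE is an AE occurring during any study phase".

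SAE rates are part of the primary outcome (Protocol 2.1, SAP 1.1.1). The SAP also tabulates an event rate for "Any AE leading to discontinuation of investigational product" (SAP 4.2.1.1).

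**The concern.** The third paragraph of 6.6.6, taken literally, stops a serious laboratory deterioration from being an AE whenever the cause is unequivocally lupus. An event that is not an AE cannot be an SAE under 6.2, so it never reaches the reporting duty in 6.7. The first paragraph of the same section, and 6.6.7 by its evident intent, would report it. The protocol does not say which rule prevails.

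At stake is whether a primary outcome is collected in the same way everywhere. The synopsis plans about 300 sites, and two of them could handle identical events differently without either deviating from the protocol. Such a discrepancy is hard to see afterwards, because the missing item is a record that was never created.

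**Working it through.** **Step 1. A test case.** A subject has no symptoms. A mandated test (Table 5 includes blood counts, creatinine and the urine protein/creatinine ratio) shows a deterioration that the investigator considers unequivocally lupus, and the subject is admitted on that finding alone. Admission is a seriousness criterion in 6.2.

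| Rule | Is it reported? |
|---|---|
| 6.6.6, first paragraph | Yes, an SAE criterion is met |
| 6.6.6, third paragraph | No |
| 6.6.7 | Yes, if its exception extends to laboratory findings; as worded it covers signs and symptoms |
| 6.7 | Yes, provided the event counts as an SAE, which under 6.2 requires it to be an AE |

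**Step 2. Can another reading remove the conflict?**

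- *The bar covers only nonserious events.* The definition in 6.1 rules this out, because AE includes serious AEs.
- *The word only in the first paragraph states a necessary condition, and the third paragraph is a further exclusion.* This makes 6.6.6 consistent with itself. It still leaves 6.6.6 dropping serious lupus events that 6.6.7 means to keep and 6.7 wants reported.

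**Step 3. Size per reclassified subject.** The plan states no figure for these events, so there is nothing to reproduce. SAP 3.1.1 defines the event rate as subjects with an event divided by total exposure, scaled to 100 subject-years. If *k* subjects change status and total exposure is *T* years, the rate moves by 100 × *k* / *T*. Planned follow-up is 893 subject-years (Randomised Anifrolumab 300 mg) and 517 (Randomised Placebo), from Protocol 8.2 and SAP 1.3.

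- One subject: 100 / 893 = 0.11 on anifrolumab; 100 / 517 = 0.19 on placebo.
- Five subjects: 500 / 893 = 0.56; 500 / 517 = 0.97.

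The rate counts subjects, so someone with another SAE in the same period stays counted and moves nothing.

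**Step 4. The contrast between groups.** Let *a* and *b* be the shares of subjects with an SAE who are lost on anifrolumab and on placebo because their only SAE is of this kind. A true rate ratio of 1.00 then reads (1 − *a*) / (1 − *b*). The documents give no value for *a* or *b*, so these are assumptions:

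- 5% and 5%: 0.95 / 0.95 = 1.00
- 1% and 5%: 0.99 / 0.95 = 1.04
- 2% and 10%: 0.98 / 0.90 = 1.09

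For scale, assume an SAE rate of 10 per 100 subject-years in both groups, that is 89.3 and 51.7 subjects. The standard error of the log ratio is √(1/89.3 + 1/51.7) = 0.175, so the 95% interval around 1.00 is exp(±1.96 × 0.175), or 0.71 to 1.41. The shifts above are small beside that.

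**Step 5. Stopping investigational product.** The first paragraph of 6.6.6 treats a mandated laboratory deterioration that is the reason for stopping as reportable. The third paragraph does not when the cause is unequivocally lupus, and 6.6.7 has no such exception either. Two rules point one way and one the other.

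**The case against.** The best reply is that very few events fall into the gap.

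- The bar applies only where the cause is unequivocally lupus. A reader might infer that every lupus-related laboratory change is barred, but equivocal cases are not.
- Where clinical signs accompany the change, the second paragraph of 6.6.6 says "the sign or symptom will be reported as an AE and the associated laboratory result/vital sign will be considered as additional information". It also prefers the clinical term to the laboratory term.
- Section 6.6.5 prefers diagnoses, and 6.5 treats class III to V lupus nephritis as an AE whose diagnosis laboratory results support. A hospitalised cytopenia or nephritis would usually be recorded under its diagnosis.
- The information is not wholly lost. Nephritis, haemolytic anaemia and hospitalisation for SLE are severe-flare criteria (SAP 3.1.5), and laboratory shifts are tabulated (SAP 4.2.1.6).

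All of this stands and narrows the point. It does not close it. A serious laboratory-only finding with no recorded sign, symptom or diagnosis is still covered by contradictory instructions, and flare and laboratory tables do not feed the SAE rate.

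On stopping product, the reply is stronger. The third paragraph of 6.6.6 and 6.6.7 can be read as one coherent convention, that lupus worsening is not an AE unless serious. AEs leading to discontinuation are also not a primary outcome.

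**Conclusion.** The collection rule for serious laboratory deterioration that is unequivocally lupus is contradictory as written, and it feeds a primary outcome. The conclusion rests on the wording of 6.1, 6.2, 6.6.6, 6.6.7 and 6.7 and needs no numerical assumption.

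The affected set is narrow, and its size cannot be found from the documents. What can be stated is the leverage of each reclassified subject whose only SAE is of this kind: about 0.11 (anifrolumab 300 mg) or 0.19 (placebo) per 100 subject-years at planned follow-up. Actual exposure will change these figures.

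Two stronger readings should be resisted.

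- A reader might infer that the bar tilts the comparison against anifrolumab, since lupus-driven events could be commoner on placebo. SAP 4.2.1 does call the comparison of the two main groups the primary assessment. But no document gives the frequency of these events in either group, equal loss leaves the ratio unchanged, and Protocol 8.2 plans no formal comparison. The ratios of 1.04 and 1.09 are illustrations from assumed shares.
- A reader might infer that 6.6.7 is in error for lacking an exception for stopping product. The documents show only that the first paragraph of 6.6.6 disagrees with the third paragraph and 6.6.7. They do not show which convention was intended.

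**What to change.** 1. In the third paragraph of 6.6.6, add the exception *unless it meets an SAE criterion*.
2. In 6.6.7, let the serious exception refer to *signs, symptoms or laboratory findings*.
3. Before lock, query lupus-related hospitalisations that have no matching SAE record. If lock is too close for amended text to help (the protocol expected the study to end by Q3 2021 and SAP v5.0 is dated April 2022), the query is the practical remedy, and the study report should state which convention was applied.
4. For lupus laboratory changes that lead to stopping investigational product, reconcile the first paragraph of 6.6.6 with the third paragraph and 6.6.7 by stating one reporting convention. Adding a discontinuation exception to 6.6.7 is a choice for the sponsor and not a required correction. It would turn stops for lupus worsening in general, laboratory or not, into AEs leading to discontinuation.

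The cost is a clause in each of two sections (or in the CRF guidance), one stated convention and one data query. No new assessments are needed.
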